6.1. Study Population

6.1.1. Inclusion Criteria

Patients may be included in the study if they meet all of the following criteria during screening prior to the first dose of study drug.

- [1] Have histologically confirmed diagnosis of unresectable locally advanced or metastatic STS, not amenable to curative treatment and after available standard therapies (per local guidelines) have failed to provide clinical benefit, or been deemed inappropriate candidates for additional standard treatments by the investigator.

Patients with a diagnosis of Grade 1 liposarcoma (atypical lipomatous neoplasms) are eligible if there is histological or radiographic evidence of evolution to more aggressive disease.

- [2] Is ≥ 18 years of age.
- [3] Are willing and able to perform written informed consent for the trial and are amenable to compliance with protocol schedules and testing.
- [4] Have measurable or nonmeasurable but evaluable disease as defined by Response Evaluation Criteria in Solid Tumors (RECIST version 1.1 [v1.1]; Eisenhauer et al. 2009).

[5] Have adequate organ function, as defined in the table below, with all screening labs performed within 14 days of first dose of study treatment.

System	Laboratory Value
Hematological	
Absolute neutrophil count (ANC)	$\geq 1.5 \times 10^9/L$
Platelets	$\geq 100 \times 10^9/L$ (platelet transfusions are not allowed within 2 weeks prior to Study Day 1, see Exclusion Criterion [20])
Hemoglobin	$\geq 9 \text{ g/dL}$ or $\geq 5.6 \text{ mmol/L}$ (packed red blood cell transfusions are not allowed within 2 weeks prior to Study Day 1, see Exclusion Criterion [20])
Renal	
Creatinine or Measured or calculated ^a creatinine clearance (CrCl) (GFR may be used in place of creatinine or CrCl) (Attachment 7)	$\leq 1.5 \times \text{ULN}$ or $\geq 60 \text{ mL/min}$
Hepatic	
Total bilirubin	$\leq 1.5 \times \text{ULN}$
AST (SGOT) and ALT (SGPT)	$\leq 2.5 \times \text{ULN}$ or $\leq 5 \times \text{ULN}$ for patients with liver metastases
Coagulation	
The patient has an adequate coagulation function as defined by International Normalized Ratio $\leq 1.5 \times \text{ULN}$ or prothrombin time $\leq 1.5 \times \text{ULN}$, and partial thromboplastin time $\leq 1.5 \times \text{ULN}$ if not receiving anticoagulation therapy. For patients receiving anticoagulants, exceptions to these coagulation parameters are allowed if they are within the intended or expected range for their therapeutic use. Patients must have no history of active bleeding (defined as within 14 days of first dose of study drug) or pathological condition that carries a high risk of bleeding (e.g., tumor involving major vessels or known esophageal varices).	

^a Creatinine clearance should be calculated per institutional standard.

[6] Have an Eastern Cooperative Oncology Group Performance Status (ECOG PS) score of 0 or 1 at the time of enrollment (refer to Attachment 6).

[7] Have sufficient available material from archived formalin-fixed paraffin-embedded tumor tissue obtained within 6 months of study enrollment CCI [REDACTED]

- [8] Have resolution, except where otherwise stated in the inclusion criteria, of all clinically significant toxic effects of prior systemic cancer therapy, surgery, or radiotherapy to Grade ≤ 1 by National Cancer Institute (NCI) Common Terminology Criteria for Adverse Events (CTCAE), Version 4.0 (v 4.0).
- [9a] If male, the patient is sterile (including vasectomy) or agrees to use an effective method of birth control (for example, male condom with spermicide) and to not donate sperm during the study and for at least 120 days following the last dose of study treatment.
- [9b] If female, is not of childbearing potential due to surgical sterilization confirmed by medical history (at least 6 weeks post-surgical bilateral oophorectomy with or without hysterectomy or tubal ligation) or menopause.

Menopausal women include women with either:

- 1) spontaneous amenorrhea for at least 12 months, not induced by a medical condition such as anorexia nervosa, and not taking medications during the amenorrhea that induced the amenorrhea (for example, oral contraceptives, hormones, gonadotropin-releasing hormone, antiestrogens, selective estrogen receptor modulators, or chemotherapy), or
- 2) spontaneous amenorrhea for 6 to 12 months and a follicle-stimulating hormone level >40 mIU/mL.

If female and of childbearing potential, has a negative serum or urine pregnancy test within 72 hours prior to the first dose of study medication, agrees to use a highly effective method of birth control during the study and for up to 120 days following the last dose of the study drugs, and is not breastfeeding. If the urine test is positive or cannot be confirmed as negative, a serum pregnancy test will be required.

A highly effective method of birth control is defined as one that results in a low failure rate (that is, $<1\%$ incidence of pregnancy per year) when used consistently and correctly, such as contraceptive implants, injectables, combined oral estrogen or progestogen-only contraceptives associated with inhibition of ovulation, some intrauterine contraceptive devices (IUDs), sexual abstinence, or a vasectomized partner. For patients using a hormonal contraceptive method, information regarding the study drugs under evaluation and their potential effect on the contraceptive should be addressed.

Abstinence as a method of birth control is acceptable if it is the established and preferred method of contraception for the patient.

- [10] Have an anticipated life expectancy of ≥ 3 months.
- [11] Inclusion Criterion [11] has been deleted.

6.1.2. ***Exclusion Criteria***

Potential study patients may not be included in the study if any of the following apply during screening.

- [12] Have disease that is suitable for local therapy administered with curative intent.
- [13] Have received any previous systemic therapy (including investigational agents) targeting PD-1/PDL-1 or PD-1/PDL-2 signaling pathways (including previous participation in Merck MK-3475 trials). Prior treatment with olaratumab is allowed. Prior therapy with other immune checkpoint inhibitors, including but not limited to, anti-CD137 antibody or anti-cytotoxic T-lymphocyte-associated antigen-4 (CTLA-4) antibody, is not permitted.
- [14] Have had chemotherapy, targeted small molecule therapy, or radiation therapy within 2 weeks and/or monoclonal antibody treatment within 4 weeks prior to study Day 1 or who have not recovered (that is, to \leq Grade 1 or baseline) from the effects of previously administered agents.
 - Neuropathy (\leq Grade 2) or nonserious and nonlife-threatening toxicities, such as alopecia, altered taste, or nail changes, are an exception to this criterion.

Note: If patient received major surgery, they must have recovered adequately from the toxicity and/or complications from the intervention prior to starting therapy.

- [15] Exclusion Criterion [15] has been deleted.
- [16] Have known active CNS metastasis and/or carcinomatous meningitis (screening not required). Patients with treated CNS metastases are eligible for this study if they have not received corticosteroids and/or anticonvulsants within 7 days of study treatment, and their disease is asymptomatic and radiographically stable for at least 60 days. This exception does not include carcinomatous meningitis, which is excluded regardless of clinical stability.
- [17] Have a history or current evidence of any serious medical condition, therapy, or laboratory abnormality that might confound the results of the trial, interfere with the patient's participation for the full duration of the trial, or not be in the best interest of the patient to participate, in the opinion of the treating investigator. Serious medical condition(s) include, but are not limited to, the following:
 - Diagnosis of immunodeficiency or is receiving systemic steroid therapy or any other form of immunosuppressive therapy within 7 days prior to the first dose of study treatment.

- Active autoimmune disease that has required systemic treatment in past 2 years from first dose of study treatment (that is, with use of disease-modifying agents, corticosteroids or immunosuppressive drugs). Replacement therapy (for example, thyroxine, insulin, or physiologic corticosteroid replacement therapy for adrenal or pituitary insufficiency, etc.) is not considered a form of systemic treatment.
- History of (non-infectious) pneumonitis that required steroids or current pneumonitis.
- Known human immunodeficiency virus (HIV) infection (HIV 1/2 antibodies) or acquired immunodeficiency syndrome (AIDS)-related illness (screening not required).
- History of interstitial lung disease.
- Known active Hepatitis A, B (for example, HBsAg reactive) or C (for example, HCV RNA [qualitative] is detected) infection (screening not required).
- Liver cirrhosis at a level of Child-Pugh B (or worse).
- Liver cirrhosis (any degree) and a history of hepatic encephalopathy or clinically meaningful ascites resulting from cirrhosis. Clinically meaningful ascites is defined as ascites resulting from cirrhosis and requiring ongoing treatment with diuretics and/or paracentesis.
- Active or uncontrolled clinically serious infection requiring systemic therapy.
- Known psychiatric or substance abuse disorders that, in the opinion of the investigator, may prevent the patient from participating in the clinical trial.
- Known allergy or hypersensitivity reaction to olaratumab or any of its components.
- Has severe hypersensitivity (\geq Grade 3) to pembrolizumab and/or any of its excipients.
- History of prior or second concurrent primary malignancies that, in the judgment of the investigator and Lilly, may affect the interpretation of results. Patients with carcinoma in situ of any origin and patients with prior malignancies who are in remission and whose likelihood of recurrence is very low (such as basal cell carcinoma), as judged by the investigator in consultation with Lilly CRP/CRS, are eligible for this study.

[18] Have received a live-virus vaccine within 30 days prior to planned treatment start. Examples of live vaccines include, but are not limited to: measles, mumps, rubella, chicken pox, yellow fever, seasonal flu, H1N1 flu, rabies, Bacillus

Calmette-Guérin (BCG), and typhoid vaccine. Seasonal flu vaccines that do not contain live virus are permitted.

- [19] Have received transfusion of blood products (including platelets or red blood cells) or administration of colony stimulating factors (including granulocyte colony stimulating factors [G-CSF], GM-CSF or recombinant erythropoietin) within 2 weeks prior to study Day 1.
- [20] Have histologically or cytologically confirmed Kaposi's sarcoma or gastrointestinal stromal tumor (GIST).
- [21] Have received treatment within 28 days of the initial dose of study drug with an investigational product or non-approved use of a drug (other than the study drug used in this study) or are concurrently enrolled in any other type of medical research judged not to be scientifically or medically compatible with this study. Patients participating in surveys or observational studies are eligible to participate in this study.
- [22] Have inflammatory bowel disease for which the patient has used immunosuppressive agents within the last 2 years.
- [23] Have had an allogenic tissue/solid organ transplant.

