- [9a] If male, the patient is sterile (including vasectomy) or agrees to use an effective method of birth control and to not donate sperm during the study and for at least 120 days following the last dose of study treatment.
- [9b] If female, is not of childbearing potential due to surgical sterilization confirmed by medical history or menopause. If female and of childbearing potential, has a negative serum or urine pregnancy test within 72 hours prior to the first dose of study medication, agrees to use a highly effective method of birth control during the study and for up to 120 days following the last dose of the study drugs, and is not breastfeeding.
- [10] Have an anticipated life expectancy of ≥ 3 months.
- [11] Inclusion Criterion [11] has been deleted.

Exclusion:

- [12] Have disease that is suitable for local therapy administered with curative intent.
- [13] Have received any previous systemic therapy (including investigational agents) targeting PD-1/PDL-1 or PD-1/PDL-2 signaling pathways (including previous participation in Merck MK-3475 trials). Prior treatment with olaratumab is allowed. Prior therapy with other immune checkpoint inhibitors, including but not limited to, anti-CD137 antibody or anti-cytotoxic T-lymphocyte-associated antigen-4 (CTLA-4) antibody, is not permitted.
- [14] Have had chemotherapy, targeted small molecule therapy, or radiation therapy within 2 weeks and/or monoclonal antibody treatment within 4 weeks prior to study Day 1 or who have not recovered from the effects of previously administered agents.

- [15] Exclusion Criterion [15] has been deleted.
- [16] Have known active central nervous system (CNS) metastasis and/or carcinomatous meningitis. Patients with treated CNS metastases are eligible for this study if they have not received corticosteroids and/or anticonvulsants within 7 days of study treatment, and their disease is asymptomatic and radiographically stable for at least 60 days.
- [17] Have a history or current evidence of any serious medical condition, therapy, or laboratory abnormality that might confound the results of the trial, interfere with the patient's participation for the full duration of the trial, or not be in the best interest of the patient to participate, in the opinion of the treating investigator.
- [18] Have received a live-virus vaccine within 30 days prior to planned treatment start.

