6.2. Summary of Study Design

Study JGDQ is an open-label, multicenter, nonrandomized, Phase 1a/1b dose-escalation study followed by cohort expansion of IV olaratumab plus pembrolizumab in patients with unresectable locally advanced or metastatic STS. Treatment cycles will be 21 days (\pm 3 days).

[figure not shown]
In the Phase 1a dose-escalation portion of the study, eligible patients will receive olaratumab 15 mg/kg (starting dose) or 20 mg/kg on Day 1 and Day 8 plus pembrolizumab 200 mg IV (fixed dose) on Day 1 of a 21-day cycle. Patients will enroll in a 3+3 fashion, according to the dose-escalation rules outlined in Section 7.2.2. No intrapatient dose escalation is permitted. Patients in any cohort who do not complete Cycle 1 treatment for reasons other than a DLT will be replaced. A minimum of 6 patients will be enrolled to the highest tolerated dose in Phase 1a. There will be a 2-week observation of the first patient at each dose level before additional patients in that cohort can be enrolled.

Upon determination of a recommended dose for olaratumab, a Phase 1b expansion cohort will open. Eligible patients will receive the recommended Phase 2 dose (RP2D) of olaratumab plus pembrolizumab in a 21-day cycle. In the Phase 1b portion, approximately 25 patients will be enrolled.

Figure JGDQ.1 illustrates the design of the trial.

The planned duration of treatment with pembrolizumab is a maximum of 35 cycles (approximately 2 years). The planned duration of treatment for olaratumab is not fixed; all patients will remain on study until confirmed progressive disease, unacceptable toxicity, or they fulfill one of the other criteria for study treatment discontinuation (Section 6.3).

The treatment period of the study includes a 30-day, 90-day, and a long-term follow-up period. The 30-day safety follow-up period begins 1 day after the patient and the investigator agree that the patient will no longer continue treatment and lasts approximately 30 days. The 90-day safety follow-up period begins 1 day after the 30-day safety follow-up period ends and lasts approximately 60 days. Thereafter, patients will enter the long-term follow-up period as detailed in the Study Schedule ([Attachment 1](#)).

^aEnroll 3 patients. If 1 patient has a DLT, enroll 3 more patients.

Abbreviations: D = day; DLT = dose-limiting toxicity; IV = intravenous; olara = olaratumab; pembro = pembrolizumab.

Figure JGDQ.1. Study design overview for Study I5B-MC-JGDQ.

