6.2.1. Study Completion and End of Trial

This study will be considered complete (that is, the scientific evaluation will be complete) at a date determined by Lilly at least 60 days after the last patient has discontinued treatment with pembrolizumab and after all study objectives are met.

The end of trial occurs after study completion and after the last patient has discontinued all study treatment and completed any applicable continued access follow-up.

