6.2.2. Continued Access Period

All patients remaining on study treatment (that is, with olaratumab only) without disease progression following study completion (at least 60 days after the last patient has discontinued treatment with pembrolizumab and after all study objectives are met) will be able to enter the continued access period of the study. The continued access period begins after study completion and ends at the end of trial. During the continued access period, patients on study treatment who continue to experience clinical benefit and no undue risks may continue to receive study treatment until disease progression, death, unacceptable toxicity, or start of new anticancer treatment. The continued access period includes a follow-up visit. The follow-up visit begins 1 day after the patient and the investigator agree that the patient will no longer continue treatment

in the continued access period and lasts approximately 30 days. If it is deemed to be in the best interest of the patient to start a new anti-cancer treatment prior to the scheduled end of the follow-up visit, the follow-up visit duration may be shortened. In this case, the follow-up assessments should be completed prior to the initiation of the new therapy.

Lilly will notify investigators when the continued access period begins.

During the continued access period, all AEs, SAEs, and any study drug dose adjustments will be collected on the case report form (CRF).

Serious adverse events will also be reported to Lilly Global Patient Safety and collected in the pharmacovigilance system (Section 8.1.2.5). In the event that an SAE occurs, additional information (such as local laboratory results, concomitant medications, and hospitalizations) may be requested by Lilly in order to evaluate the reported SAE.

Investigators may perform other standard procedures and tests needed to treat and evaluate patients; however, Lilly will not routinely collect the results of these assessments.

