6.3. Discontinuations

The reason for and date of treatment discontinuation will be collected for all patients. The date of discontinuation (for any reason) from study treatment is to be reported on the CRF.

If a patient withdraws informed consent, he or she must not be contacted unless he or she has explicitly provided permission and consent. Lilly may continue to use previously collected medical research data prior to the withdrawal, consistent with the original authorization.

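### Inclusion criterion [9b] words women's post-dose contraception as a ceiling of 120 days, where [9a] sets a 120-day floor for men, and no visible text gives women a minimum

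*Protocol*

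**What the plan says.** Two adjacent inclusion criteria deal with contraception.

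- **Men, [9a]** (Synopsis and Section 6.1.1): effective birth control and no sperm donation during the study and "for at least 120 days following the last dose of study treatment".
- **Women of childbearing potential, [9b]** (Section 6.1.1): highly effective birth control during the study and "for up to 120 days following the last dose of the study drugs". The Synopsis has the same text: the patient "agrees to use a highly effective method of birth control during the study and for up to 120 days following the last dose".

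The rest of [9b] covers the pregnancy test before the first dose, breastfeeding, what counts as a highly effective method, and abstinence. It says nothing more about duration.

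Section 6.2 bears on what *during the study* means: "The treatment period of the study includes a 30-day, 90-day, and a long-term follow-up period".

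**The concern.** The two criteria use the same number of days with opposite bounds. *At least 120 days* can be met only by reaching day 120. *Up to 120 days*, read literally, is met by any period from 0 to 120 days. The looser wording applies to the patients who could themselves become pregnant while study drug is still in the body, and the protocol gives no reason for a lesser duty on women.

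This is an operative safety undertaking that each woman of childbearing potential gives at screening, not background text. If the wording is taken at face value, a site or a patient could regard the obligation as discharged before most of the antibody has cleared.

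**Working it through.** The plan has no figure to reproduce here. The check is a comparison of texts, followed by a short calculation of scale.

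**Step 1. Is the difference real and current?** Yes. [9a] and [9b] differ in the same way in the Synopsis and in Section 6.1.1. The Amendment (c) summary shows no change to either criterion.

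**Step 2. Does other text supply a minimum for women?** None that is visible.
- Section 8.1.2 covers reporting of pregnancies and removal from treatment.
- The Attachment 1 schedule lists pregnancy tests, including at safety follow-up Visits 801 and 802, but gives no contraception period. Its comments column is blank or redacted in the supplied text.
- The SAP does not address contraception.

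**Step 3. Does *during the study* close the gap?** It depends on how the phrase is read.
- *Narrow reading (treatment only).* No post-dose minimum is stated for any woman.
- *Broad reading (follow-up included, as Section 6.2 suggests).* A woman still in follow-up at day 120 is covered. The gap is then limited to women whose participation ends sooner. Examples, not a complete list:
  - Consent withdrawal (Section 6.3): "If a patient withdraws informed consent, he or she must not be contacted unless he or she has explicitly provided permission and consent".
  - Loss to follow-up (Section 6.3.3).
  - Closure of the study by the sponsor (Section 6.3.5), or study completion (Section 6.2.1), which may fall "at a date determined by Lilly at least 60 days after the last patient has discontinued treatment with pembrolizumab", once objectives are met.
  - Continued access (Section 6.2.2), where the follow-up visit begins after the decision to stop treatment "in the continued access period and lasts approximately 30 days".

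The number of uncovered days cannot be fixed for each of these. For example, the study-completion date is tied to stopping pembrolizumab, while [9b] counts from the last dose of the study drugs, and olaratumab may continue after pembrolizumab stops (Section 6.3.2).

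**Step 4. How much drug remains?** Inputs: pembrolizumab terminal half-life 27 days, CV 38% (Section 5.3.2.2). Assumption: single-exponential decline after the last dose. Formula: fraction remaining = 0.5^(t / half-life).

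| Half-life | Day 30 | Day 120 |
|---|---|---|
| 27 days (geometric mean) | 0.5^(30/27) = 0.463 | 0.5^(120/27) = 0.046 |
| 27 × 1.38 = 37.3 days (one CV longer) | 0.5^(30/37.3) = 0.57 | 0.5^(120/37.3) = 0.11 |
| 27 × 0.62 = 16.7 days (one CV shorter) | 0.5^(30/16.7) = 0.29 | 0.5^(120/16.7) = 0.007 |

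On the typical half-life, the fraction remaining at day 30 is about ten times that at day 120 (0.463 / 0.046 = 10.1).

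The day-30 pembrolizumab figure does not carry over to continued access, which is described as "All patients remaining on study treatment (that is, with olaratumab only) without disease progression following study completion". For olaratumab, with a half-life of about 11 days (Section 5.3.2.1), the day-30 fraction is 0.5^(30/11) = 0.15.

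**The case against.** The strongest reply is that [9b] is an undertaking, and in an undertaking *up to 120 days* can mean *through day 120*. A reading that permits zero days would leave the number with no purpose. This is probably what was meant. The protocol's own usage does not settle it, however. The 14-day limit on treatment delay (Section 7.2.4.1) and the 6-hour room-temperature allowance (Section 7.1.2) are clearly caps, while the 24-week imaging period (Section 8.3) reads more like *through*. With the unambiguous form in the neighbouring criterion, a safety commitment should not depend on which sense a site adopts.

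A second reply is that a woman's actual instruction is in the consent form, which was not available, and that some schedule comments are also missing. That stands as a limit: the statement that no minimum is given applies only to the visible text. A consent form with the right period would protect the patient but would then differ from the protocol criterion.

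A third reply is that no consequence is shown. Pregnancy tests run through the safety follow-up to about day 90, pregnancies during exposure are reportable, and the number of women of childbearing potential among the roughly 37 patients is unknown. All of this stands and is why the point is minor.

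A reader might infer that the protocol deliberately allows women to stop contraception at the last dose, or that fetal harm has been shown. The documents support neither. The wording is most likely a slip, and the percentages describe residual drug only.

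**Conclusion.** The point holds as a minor drafting error. [9b] literally states a maximum, [9a] states a minimum, and no visible text gives women a 120-day minimum. On the broad reading of *during the study*, the gap affects only women whose participation ends before day 120. On the narrow reading, it affects every woman of childbearing potential.

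The scale, for a typical pembrolizumab half-life and single-exponential decline, is about 46% of the end-of-treatment level at day 30 against about 5% at day 120. It might be tempting to treat these as upper limits. They are not: with a CV of 38%, a half-life one CV longer leaves about 57% and 11%. Nor do the documents support a complete list of early-exit routes, or a fixed number of missing days for each.

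The conclusion itself rests on the text and does not depend on the half-life calculation. No endpoint, sample size or planned analysis is affected.

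**What to change.** In [9b], replace *up to* with *at least*, in the Synopsis and in Section 6.1.1, so that it matches [9a]. Check the consent form for the same phrase and align it if needed.

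The cost is one two-word replacement made in two places at the next amendment, plus the consent-form check. If 120 days was always intended, the change only makes that explicit.
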